3.4.1 Clinical Forms and Interview Schedule

Measure/Test	Form Details	Baseline/ Presurgery	6 month follow up	12 month follow up	18 month follow up	annual follow up
PSYCHOPATHOLOGY N= 250						
INTERVIEW						
SCID/IP	Structured Clinical Interview for DSM-IV	X				X
EDE- BSV	Eating Disorders Examination- Bariatric Surgery Version	X		X		X
M-FED-BSV	MFED- Bariatric Surgery Version	X	X	X	X	
SELF-REPORT						
BDI*	Beck Depression Inventory	X	X	X		X
SF-36*	Short Form-36	X	X	X		X
IWQOL- Lite	Impact of Weight on Quality of Life- Lite	X*	X	X*		X*
PETS	Psychiatric and Emotional Test Survey	* X	X	* X	X	* X
MED	Medication Form	* X	* X	* X	X	* X
CTQ	Childhood Trauma Questionnaire					X (one time)
EATING BEHAVIOR N= 100						
NDS	48 Hour Dietary Recall- Nutritional Data System	X	X	X		X

* Gathered as a part of LABS-2

INTERVIEW SCHEDULE WITH NEW MEASURES AND TASKS AT YEAR 7:

LABS Baseline and F/U Funding for Part of Cohort						RO1 Funding				
	Pre-surg	6 mo	1 yr	18 mo	2 yrs	3 yrs	4 yrs	5 yrs	6 yrs	7 yrs
INTERVIEW										
SCID/IP	X				X	X	X	X	X	X
EDE-BSV	X		X		X	X	X	X	X	X
M-FED-BSV		X	X	X	X	X	X	X	X	X
72-hour dietary recall (NDS-R)	X	X	X		X	X	X	X	X	X
SELF-REPORT										
Administered as a part of LABS 2*	X	X	X	X	X	X	X	X	X	X
The following have been added as a new, separate final visit.										
DERS										X
AIM										X
UPPS-P										X
ATQ-ECS										X
SPSRQ										X
Go/No-Go Task										X
Delay Discounting Task										X

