c. Hypothesis #3. Hypothesis #3 states that untreated psychopathology at the time of bariatric surgery will be associated with increased short-term complications. A logistic regression analysis will be used to evaluate the influence of psychopathology at the time of surgery on short-term surgical complications. Analyses will evaluate the impact upon both DSM-IV diagnostic psychopathology (e.g., current mood disorder, current anxiety disorder, current substance use disorder, any Axis I disorder, any Axis II disorder) and a continuous measure of depressive symptoms, the BDI, upon short-term post-surgical complications.

d. Hypothesis #4. Hypothesis #4 posits that syndromal or subsyndromal eating disorders prior to surgery will be associated a greater frequency of eating disorder symptoms and less weight loss at long-term follow-up. Data from the EDE-BSV and the NDS dietary recall will be aggregated to determine the frequency of various eating disorder symptoms (binge eating, grazing, vomiting, chewing and spitting) at each assessment point. RRM's will then be used to evaluate the effect of pre-surgical eating disorder syndromes (including binge eating disorder and night eating) on eating disorder frequency (Poisson-based RRM) and BMI (linear RRM). The basic models will include a random effect for subject, and fixed effects for site, assessment time, time-by-site interaction, and pre-surgical eating disorder diagnoses (both syndromal and subsyndromal diagnoses).

Power Analysis and Sample Size

Hypothesis #1. Power analyses below assume an attrition rate of 15% at 12 months, and a 10% attrition rate at 24 month assessments. An enrolled sample size of 250 would provide an estimated sample size of 213 at 12 months and 191 at 24 months.

Power analyses regarding the reduction of psychopathology following surgery is based on the finding of Glinski et al. (2001) that 50% of pre-bariatric surgery candidates meet criteria for at least one current Axis I disorder. Assuming a conservative two-tailed alpha of .01, the proposed sample size would provide a power of .90 to detect a reduction in psychopathology of just over 10% from pre-surgery at 12 months and 12% at 24 months (Hintze, 2001). These reductions for Axis I disorders are consistent with those reported in the literature following bariatric surgery (Herpetz et al. 2004).

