Hypothesis #3. Power analysis estimates for Hypothesis #3 are based upon a study by Powers et al. (1988) reporting an association between the presence of pre-surgery Axis I diagnosis and post-surgical complications. All 9 (100%) patients with a pre-surgical Axis I diagnosis experienced post-surgical complications, compared to 7 of 15 (47%) of those without a pre-surgical Axis I diagnosis (contingency coefficient = .42). It would be unrealistic to expect that every patient with an Axis I disorder would develop post-surgical complications. However, if we assume that 80% of those with an Axis I disorder would develop complications post-surgery, and further assume a conservative two-tailed alpha of .01, the proposed sample size of 250 enrolled patients would provide a power of .98 to detect this association and would provide a power of .80 to detect a contingency coefficient of .165 (Hintze, 2001).

Hypothesis #4. Power analysis for Hypothesis #4 is based upon a study of Hsu et al. (1996) reporting an association between pre-surgical eating disturbance and weight regain post-surgery. They report that 8 of 19 (42%) patients with pre-existing eating disturbance regained weight after surgery, compared to 0 of 5 (0%) without a pre-existing eating disturbance (contingency coefficient = .341), corresponding to an effect size (d) of .57. Power analyses assume a conservative two-tailed alpha of .01, a 50% rate of pre-surgical eating disturbance, and 5 observation points (6, 12, 18 and 24 months), and a correlation of .30 between observations. Power analyses focus on the differences weight loss between those individuals with and without pre-surgical psychopathology. The proposed sample size of 100 subjects for the assessment of eating behavior will provide a power of approximately .88 to detect an attrition-adjusted effect size of .57 (Hedeker et al., 1999).

5 Study Organization

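### Hypothesis 4 builds its symptom count from two instruments that differ in participants, visits and content, although the EDE-BSV alone covers every listed symptom in all 250

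*Protocol*

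**What the plan says.** Section 4, Hypothesis #4, defines the symptom outcome in one sentence: "Data from the EDE-BSV and the NDS dietary recall will be aggregated to determine the frequency of various eating disorder symptoms". The symptoms and timing follow: "binge eating, grazing, vomiting, chewing and spitting) at each assessment point". The effect of pre-surgical eating disorder status is then modelled "on eating disorder frequency (Poisson-based RRM) and BMI (linear RRM". The text gives no rule for combining the two sources and names no analysis set.

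In the first schedule table of section 3.4.1 the EDE-BSV stands under "PSYCHOPATHOLOGY N= 250" and the recall under "EATING BEHAVIOR N= 100". The Design Synopsis describes the 100 as a subset. That table calls the recall "48 Hour Dietary Recall- Nutritional Data System"; the second table of the same section calls it "72-hour dietary recall (NDS-R".

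Section 3.4.2 makes the EDE the primary measure of eating behaviour and pathology. It lists binge eating, grazing, vomiting, and chewing and spitting among what the EDE-BSV quantifies, and adds night eating. Section 3.4.4 describes the NDS-R as a nutrient system that assesses food intake over 24-hour intervals.

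The Hypothesis 4 power paragraph, which concerns weight, uses "The proposed sample size of 100 subjects for the assessment of eating behavior" and reports power of about .88.

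**The concern.** A longitudinal count has to mean the same thing for every person and at every visit. Here the two contributing instruments are not taken in the same people or at the same visits, and only one of them is described as recording the symptoms. Two outcomes are possible, and they are alternatives:

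- If whatever is available is used, the count rests on both sources for 100 people and on one for 150. Within the 100, its source also changes between 6 and 12 months. A change of source can then look like a change in symptom frequency, in a model whose purpose is to describe that frequency over time.
- If both instruments are required, the symptom analysis shrinks to the 100 and has no 6-month value.

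The BMI part of the hypothesis is affected differently. It needs nothing from the NDS, yet its power is computed on the NDS subset, so the set of people meant for that model is unclear.

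**Working it through.** **1. The instruments side by side** (sections 3.4.1, 3.4.2 and 3.4.4)

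| | EDE-BSV | NDS recall |
|---|---|---|
| Participants | 250 | 100 (subset) |
| Baseline | yes | yes |
| 6 months | no | yes |
| 12 months | yes | yes |
| 18 months | no | no |
| Annually from 24 months | yes | yes |
| Described content | all four listed symptoms | food intake |
| Period covered | not stated | 48 h in one table, 72 h in the other |

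A combined count is therefore unavailable at 6 and 18 months for everyone. For 250 − 100 = 150 people (150/250 = 60%) it is unavailable at every visit. At 6 months the NDS is the only one of the two sources. As described, it supplies no count of vomiting or of chewing and spitting.

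**2. The recall length.** Both tables mark the recall from before surgery onward, so the difference is not simply a later change for the extension. At an unchanged true rate, a raw recall-based count is 72/48 = 1.5 times larger under the longer window. This matters only if raw counts from different windows are mixed.

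**3. What the BMI model needs.** It needs pre-surgical eating disorder status and BMI. The diagnostic EDE-BSV is in the N = 250 block at baseline. Weight comes from the LABS-2 database (section 3.4). Neither depends on the NDS.

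**4. The stated power of .88.** Inputs from section 4: d = .57, two-sided alpha .01 (z = 2.576), correlation ρ = .30 and equal groups. The attrition in the Hypothesis 1 paragraph gives retention of .85 at 12 months and .85 × .90 = .765 at 24 months. The power paragraph says five observation points but lists four, so both are tried. For a difference averaged over m visits:

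power = Φ( d·√[ (N/2) / (2(1 + (m−1)ρ)/m) ] − 2.576 )

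With 100 × .765 = 76.5 completers:
- m = 5: 2 × 2.2/5 = .88; √(38.25/.88) = 6.593; .57 × 6.593 − 2.576 = 1.18; power **.881**.
- m = 4: 2 × 1.9/4 = .95; √(38.25/.95) = 6.345; .57 × 6.345 − 2.576 = 1.04; power **.851**.

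With m = 4 and people lost in stages, power is .872 to .900. This assumes retention of .925, .85, .8075 and .765, or .85, .85, .765 and .765, at the four visits; the 6- and 18-month values are assumptions. With no attrition and m = 4 it is .940. The stated .88 is reproduced.

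**5. The same calculation with all 250.** Completers: 250 × .765 = 191.25.
- m = 4: √(95.625/.95) = 10.033; .57 × 10.033 − 2.576 = 3.14; power **.9992**.
- m = 5: √(95.625/.88) = 10.424; .57 × 10.424 − 2.576 = 3.37; power **.9996**.
- One follow-up visit only: √(95.625/2) = 6.915; .57 × 6.915 − 2.576 = 1.37; power **.914**.

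On completers, the difference detectable with power .88 falls from d = .57–.59 (N = 100) to d = .36–.37 (N = 250), in line with √(100/250) = .63.

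**6. The symptom count.** No event rates are given, so power for the Poisson model cannot be computed. The d of .57 comes from weight regain and does not carry over to it.

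**The case against.** The strongest reply is that the text does less harm than it seems to. Four parts of it deserve an answer.

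- *The protocol does not discard 150 people.* This is correct. A reader might infer the exclusion from the N = 100 in the power paragraph, but a sample size calculation is not an analysis-set rule, and the BMI model needs nothing from the NDS. For the symptom count, the loss follows only if both instruments are required.
- *Aggregating need not mean adding.* It could mean using recalled intake to corroborate or classify episodes, for instance whether a large amount was eaten. That is possible, but corroboration would still be available for only 100 of 250 people and would have no EDE-BSV report to corroborate at 6 months.
- *The 1.5 factor may never arise.* Each table gives a single window for all its visits, and section 3.4.4 describes 24-hour intervals, which permit scaling per day. This stands: the factor is the size of the discrepancy, not a demonstrated bias. A mismatch between EDE-BSV and NDS windows cannot be sized at all, because no EDE-BSV reference period is given.
- *Exposure terms and analysis sets belong in a SAP.* That is fair for an offset, and its absence is not the point here. The aggregation rule, however, is written in the protocol and conflicts with the protocol's own schedule and instrument descriptions. A SAP that followed it would inherit the conflict.

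**Conclusion.** The point holds as a defect in how the Hypothesis 4 symptom outcome is defined, together with an unclear analysis set and a contradiction over the recall length. As scheduled, the two instruments cannot give one consistent count at each assessment point. Either the source varies across people and visits, or the symptom analysis loses 60% of the cohort. These harms are alternatives and should not be added together.

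A reader might also infer that the power of .88 is wrong or that the hypothesis is underpowered. The documents do not support that: on the protocol's own inputs .88 is reproducible at N = 100 for an averaged contrast. What is at stake for BMI is precision that is already available: power of at least .999 instead of about .85 to .90, or a detectable d of about .36–.37 instead of .57–.59. These figures rest on d = .57, ρ = .30, equal groups, four or five visits and the stated attrition. They describe a constant group difference, which is the form of the section 4 model; that model has no diagnosis-by-time term. The effect on the symptom analysis cannot be put into a power figure.

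**What to change.** In section 4, Hypothesis #4:

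1. Define symptom frequency from the EDE-BSV alone, in all 250, at its scheduled visits (baseline, 12 months and annually). State the period the count covers and put all counts on one common time scale.
2. State that the BMI model uses all 250, and align the N in the power paragraph with that.
3. Make NDS intake a separate analysis in the 100, expressed per day.
4. Reconcile the 48-hour and 72-hour entries in the two tables of section 3.4.1. If the length did differ between visits or participants, record when and for whom.

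No new data are needed; the cost is wording. The one downside is that there is no symptom outcome at 6 months, a visit at which the EDE-BSV is not scheduled.

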**Longitudinal Assessment of Bariatric Surgery (LABS-3):
Psychosocial Issues and Bariatric Surgery**

Design Synopsis

Hypotheses

1. Patients undergoing bariatric surgery will experience significant decreases in the rates of psychopathology, in particular depressive illness, and significant improvements in quality of life, post-operatively.
2. Untreated psychopathology that persists well beyond the surgery (e.g. to one-year follow-up) or that develops post-operatively will be associated with less weight loss and decreased quality of life.
3. Untreated psychopathology at the time of bariatric surgery, including affective disorders and substance abuse/alcohol abuse will be associated with increased short-term (e.g. 90 day) complications (e.g. problems with plugging, vomiting, and dehydration)
4. Syndromal/subsyndromal eating disorders prior to surgery including binge eating disorder and night eating syndrome will be associated with eating disorder symptoms and less weight loss at long-term follow-up.
5. Greater levels of affect dysregulation, greater deficits in cognitive control and greater deficits in reward processing will be associated with less favorable outcomes (higher affective disorder rates, less favorable net weight change, and increased eating disorder pathology/alcohol use pathology) following surgery.

Type of Study

- Prospective cohort study done at three (3) LABS centers.

Inclusion Criteria

- Male and female patients who are at least 18 years of age and undergo bariatric surgery by a LABS certified surgeon.
- Previous enrollment in LABS-1 and LABS-2.
- BMI at baseline of greater than or equal to 35.

Exclusion Criteria

- Informed consent not obtained
- Type 1 Diabetes Mellitus
- Unlikely to comply with follow-up protocol (ie: geographically inaccessible for study visits)
- Unable to communicate with local study staff

Sample Size

- In order to sample a sufficient number of subjects with significant psychopathology at baseline, the sample size for the assessment of psychopathology is 250. The assessment of eating behavior will be done on a subset of 100 subjects.

Duration of Follow-up

- Up to 7 years following bariatric surgery

Outcomes

- Changes in medical and psychosocial measures

Data Collection Schedule

- The LABS-3 Psychosocial baseline data will be collected within 30 days prior to bariatric surgery.

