2.1 Primary Objective. Despite the obvious impact of bariatric surgery procedures on intake, no study to date has included a careful assessment of psychological factors, feeding patterns, energy intake and eating problems in this group of patients longitudinally. We believe that a careful examination of the structure of eating behavior and eating problems (e.g. vomiting) would be very helpful in guiding bariatric surgeons and dieticians who work with this group of patients in terms of dietary advice and recommendations, and with the prediction of eating problems and poor nutrient intake in the subgroup that develops such problems. This study involves prospective assessment of psychosocial outcomes of surgery by adding a supplemental battery to the LABS-2 assessment schedule. Conducting assessments at three of the LABS clinical sites assures the geographic, ethnic, and racial diversity of the sample, and hence

enhances the potential to identify a subgroup or subgroups of patients susceptible to poor outcomes after surgery and the generalizability of study results.

This study would also include an evaluation of psychopathological and behavioral variables that might impact on weight loss and weight regain, and psychosocial complications post-operatively, as well as quality of life.

The overall goal of this study is to obtain detailed information that will allow a careful assessment of psychopathology, quality of life and eating behavior pre-surgically and at regular intervals for up to 7 years after the surgical intervention.

Clearly subjects will have additional burden placed on them in terms of measurement; however, strategies will be used to minimize the fatigue to participants by spreading testing over several days. The staff will be cognizant of this risk. The protocol will take 3 hours in the clinic (or by phone) at certain times (baseline, 12 months and annually), and 30 minutes at 6 and 18 months, an additional hour of time will be required at the 7 year time point for the additional measures and tasks. Because of these time demands, the subjects being interviewed will be given frequent breaks.

We believe that the time points selected will allow us to examine changes midway through and at the end of the first year when many of the positive effects of the surgery will become obvious and then at 18 to 24 months when weight regain will begin to reoccur and certain psychopathological changes may reemerge in a subset of patients.

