a. Hypothesis #1. Hypothesis #1 posits that patients undergoing bariatric surgery will experience significant decreases in rates of psychopathology and quality of life. This hypothesis will be evaluated using a linear RRM (Gibbons, et al., 1988; Gibbons, et al., 1993; Bock, 1983) for depression (BDI total score) and quality of life (IWQOL-Lite total, SF-36 mental and physical component). A logistic RRM (Stiratelli, et al., 1984) will be used for psychopathology (current mood disorder, current anxiety disorder, current substance use disorder). All of the basic models will include a random effect for subject, and fixed effects for site, assessment time, and time-by-site interaction. Additional variables may include relevant covariates and missing data patterns. Bonferroni contrasts will be used to compare mean scores (for depression and quality of life) or rates of psychopathology between pre-surgical and subsequent assessment points. Analyses will include data from all participants completing at least one post-surgery assessment.

b. Hypothesis #2. Hypothesis #2 states that untreated psychopathology that persists beyond surgery will be associated with less weight loss and poorer quality of life. The effects of post-surgical psychopathology upon weight loss and quality of life will be evaluated using linear RRM's. The basic models will include a random effect for subject, fixed effects for baseline assessment, assessment time, and time-varying covariates for psychopathology (current mood disorder, current anxiety disorder, current substance use disorder, any Axis I disorder). The main effect for assessment time will be used to evaluate within-person change. The use of time-varying covariates for psychopathology allows for the possibility that a given diagnosis may be present for a given subject at one time point but absent at another. Outcome measures for these analyses for weight loss will be BMI, and for quality of life will include the IWQOL-Lite total and SF-36 mental and physical components.

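### As written, the Hypothesis 4 symptom model includes the pre-surgical visit that helps define the exposure, and its pooled main effect does not test long-term follow-up

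*Protocol*

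**What the plan says.** The Design Synopsis states that eating disorders present before surgery "will be associated with eating disorder symptoms and less weight loss at long-term follow-up". Section 4 repeats the target in the Hypothesis #4 paragraph as a "greater frequency of eating disorder symptoms and less weight loss at long-term follow-up".

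The same paragraph then sets out the analysis. "Data from the EDE-BSV and the NDS dietary recall will be aggregated" to give the "frequency of various eating disorder symptoms (binge eating, grazing, vomiting, chewing and spitting) at each assessment point". Random regression models are to "evaluate the effect of pre-surgical eating disorder syndromes (including binge eating disorder and night eating) on eating disorder frequency (Poisson-based RRM"). The basic models carry a random subject effect and "fixed effects for site, assessment time, time-by-site interaction, and pre-surgical eating disorder diagnoses (both syndromal and subsyndromal diagnoses"). No diagnosis-by-time term, baseline symptom covariate or limit to post-surgical visits is listed.

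Both tables in Section 3.4.1 schedule the EDE-BSV and the NDS before surgery. Section 3.4.2 makes the EDE the main measure of eating pathology and also the source of binge eating frequency.

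**The concern.** The exposure is a diagnosis made before surgery. If the pre-surgical symptom count is also a row of the outcome, diagnosed patients score higher on that row partly by definition, at least for binge eating. A single diagnosis coefficient averaged over all visits absorbs that difference. The model could then report that a pre-surgical eating disorder predicts symptoms when the two groups are identical at every visit after the operation.

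There is a second mismatch. Even without the pre-surgical row, a coefficient pooled over visits mixes early with late follow-up, whereas the hypothesis concerns long-term follow-up.

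**Working it through.** **1. Is the pre-surgical visit an assessment point?** The Hypothesis #1 paragraph of Section 4 compares the pre-surgical with the subsequent assessment points, so the protocol's own usage includes it. Hypothesis 4 takes over Hypothesis 1's site, time and time-by-site terms, and in Hypothesis 1 the pre-surgical value is an outcome row. Hypothesis 2 handles baseline differently, with "fixed effects for baseline assessment, assessment time, and time-varying covariates for psychopathology". That option was known to the authors and is not listed for Hypothesis 4.

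**2. Does the stated power settle it?** Inputs from the Hypothesis #4 power paragraph: N = 100, d = .57, two-sided alpha .01, correlation .30, power about .88. Attrition from the Hypothesis #1 power paragraph: 100 × 0.85 = 85, then 85 × 0.90 = 76.5.

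Power = Φ(d / √[4(1 + (m − 1)ρ)/(mN)] − 2.576).

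- Five points, 76.5 patients throughout: √[4 × 2.2/(5 × 76.5)] = 0.1517; 0.57/0.1517 = 3.76; power = .881.
- The four listed months (6, 12, 18, 24), with visit-specific numbers interpolated as 92.5, 85, 80.75 and 76.5: power = .885.
- The same four plus a pre-surgical visit with 100 patients: power = .92.

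The first two both reproduce .88. The paragraph says five points but names four, all after surgery, and it concerns weight loss. It does not settle which rows enter the symptom model.

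**3. Arithmetic of the pooled effect.** Let b1 and b0 be the mean pre-surgical counts in diagnosed and undiagnosed patients, and f the mean at each of k follow-up visits, equal in both groups, so that Hypothesis 4 is false. The pooled rate ratio is

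(b1 + kf) / (b0 + kf),

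which exceeds 1 whenever b1 > b0. The EDE-BSV is scheduled pre-surgery, at 12 months and annually, so k = 2 to 24 months and k = 7 to year 7.

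**4. Simulation.** Assumptions not in the documents: b0 = 2, f = 1, b1 equal to 1, 2 or 4 times b0, subject standard deviation 0.8 on the log scale, no attrition, no site terms. From the protocol: N = 100, half exposed, alpha .01. The model was a Poisson random-intercept model with visit effects and a diagnosis main effect, with 200 runs per scenario.

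| k | b1/b0 | Ratio by formula | Simulated ratio, pre-surgical row in | Rejection, row in | Rejection, post-surgical rows only |
|---|---|---|---|---|---|
| 2 | 1 (control) | 1 | 1.01 | 0.5% | 1% |
| 2 | 2 | (4+2)/(2+2) = 1.50 | 1.50 | 35.5% | 1% |
| 2 | 4 | (8+2)/(2+2) = 2.50 | 2.54 | 100% | 0% |
| 7 | 1 (control) | 1 | 0.98 | 2.5% | 3% |
| 7 | 2 | (4+7)/(2+7) = 1.22 | 1.21 | 12.5% | 3% |
| 7 | 4 | (8+7)/(2+7) = 1.67 | 1.69 | 74.5% | 1.5% |

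The simulated ratios agree with the formula. With post-surgical rows only, the ratio stayed between 0.98 and 1.01. At a true 1% rate, 200 runs give a standard error of √(0.01 × 0.99/200) = 0.7 percentage points. Rates of 2.5% to 3% are therefore a little high, but small beside 12.5% to 100%.

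**The case against.** The strongest objection is that no sentence says outright that the pre-surgical count is an outcome row. The phrase about each assessment point describes how a variable is built, the paragraph states its target as long-term follow-up, and the power text lists only post-surgical months. This stands as a limit: inclusion is inferred from usage and schedule. It does not remove the point, because nothing listed excludes that row or adjusts for it.

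A second objection is that these are only basic models and that an analysis plan may add contrasts. That would be fair if the protocol were silent. It names the visits and the model terms, and as stated they do not match the hypothesis.

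Three stronger readings are tempting, and the documents do not support them.

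- A reader might infer that the whole symptom outcome is circular. The overlap is direct only for binge eating. Night eating is an exposure but not a listed outcome symptom, and grazing, vomiting, and chewing and spitting do not directly define a named exposure. The paragraph also does not name the diagnostic source, and the SCID too is given before surgery. A binge eating disorder diagnosis from either interview would still go with higher pre-surgical binge counts.
- A reader might infer from Table 1 that binge eating is nearly absent at 12 months, so that this visit must be removed. The two rows with 12-month follow-up show 71% and 55%; the rows at 0% to 7% are at other times.
- A reader might infer that long-term means 24 months onward. Section 2.1 expects change "at 18 to 24 months when weight regain will begin to reoccur and certain psychopathological changes may reemerge in a subset of patients", but it does not name eating symptoms, and the protocol does not define long-term. Dropping the pre-surgical row cures the circularity without that cut-off.

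**Conclusion.** The point holds on the text as written. The Hypothesis 4 symptom model does not exclude the pre-surgical visit, and its only diagnosis term is pooled over visits. For binge eating, part of the exposure definition therefore re-enters as outcome, and the test can be significant with no post-surgical association. Nor does it isolate the long-term period that the hypothesis names.

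The direction follows from the algebra whenever diagnosed patients have more baseline symptoms. The size does not: about 13% to 100% rejection against a nominal 1%, with apparent rate ratios of about 1.2 to 2.5, rests on the assumed counts, the subject variance and 2 or 7 follow-up visits. The distortion shrinks as follow-up visits are added but was still present with seven. Since the four symptoms are not equally affected, the figures apply to an outcome whose baseline really differs by the assumed factor.

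**What to change.** State that the Hypothesis 4 symptom outcome uses post-surgical visits only. Base the conclusion on a diagnosis-by-time contrast, or a restriction of the outcome, at a long-term visit or visits that the sponsor names in advance. From 24 months onward is one option, being the first EDE-BSV visit within the window that Section 2.1 describes.

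This is a wording change to one paragraph of Section 4 and needs no new data. The small downside is fewer outcome rows in the confirmatory model, and so somewhat less precision.
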